#### **6.4.2.3 Objective Response Rate in Soft Tissue Lesions**

The analysis population for objective response rate (ORR) will be all patients in the ITT population with measurable soft tissue lesions at baseline.

ORR is defined as the proportion of patients who had a confirmed response in soft tissue lesions. An estimate of ORR will be calculated for each treatment arm, and its 95% CI will be calculated using the Clopper Pearson method. The CI for the difference in ORRs between the two treatment arms will be determined using the normal approximation to the binomial distribution.

#### **6.4.3 Exploratory Efficacy Endpoints**

The methodologies outlined for the ORR in soft tissue lesions analysis will be used for the DCR analysis.

The following exploratory time-to-event endpoints will be analyzed using the same methods as outlined in the section on secondary time-to-event endpoints.

- Modified PFS based on radiographic disease progression and unequivocal clinical progression
- DOR in soft tissue lesions
- Time to initiation of next systemic anti-cancer therapy
- Time to unequivocal clinical progression

DOR will be assessed in patients who had an objective response in soft tissue lesions as determined by the investigator.

DOR is defined as the time from the first occurrence of a CR or PR (whichever status is recorded first) until the first date progressive disease or death is documented, whichever occurs first. Patients who have not progressed and who have not died at the time of

analysis will be censored at the time of last tumor assessment date. If no tumor assessments were performed after the date of the first occurrence of a CR or PR, DOR will be censored at the date of the first occurrence of a CR or PR plus 1 day.

The statistical methods applied to DOR will be the same as for rPFS described above. However, it should be noted that DOR is evaluated in a non-randomized subset of patients (those who achieved an objective response in soft tissue); therefore, results of this analysis will be provided for descriptive purposes only.

#### **6.4.4            Subgroup Analyses**

Subgroup analyses will be performed in an exploratory manner in order to investigate consistency of the treatment effect across different subgroups. Subgroup categories will include demographic characteristics (e.g., age, sex, and race/ethnicity), baseline disease characteristics (e.g., prior taxane-containing therapy, type of disease progression [PSA only vs. radiographic disease progression], sites of metastases), and stratification factors, and other subgroups as appropriate.

Subgroup analyses will use similar methods as those used for the study population as a whole. Results for efficacy parameters in subgroups will be presented in Forest plots and descriptive summary tables.

It is not planned to investigate the homogeneity of the treatment effect across individual centers because with approximately 180 recruiting centers the average number of patients per center would be too small to detect any meaningful differences between them.

Additional details will be provided in the Statistical Analysis Plan (SAP) prior to performing the analyses.

#### **6.5                SAFETY ANALYSES**

Safety analyses will be performed on the safety-evaluable population, which is defined as all randomized patients from the global enrollment phase who receive any amount of any component of study treatments. Patients will be summarized according to the treatment actually received. Specifically, for patients randomized to the enzalutamide alone arm, if atezolizumab was received by mistake, patients will be grouped under the atezolizumab arm in the safety analyses.

Exposure to study treatment will be summarized to include treatment duration, number of doses, and dose intensity.

Verbatim description of adverse events will be coded to MedDRA preferred terms and graded according to NCI CTCAE v4.0. All adverse events occurring during or after the first study-drug dose will be summarized by treatment arm and NCI CTCAE grade. In addition, serious adverse events, Grade  $\geq$  3 adverse events, adverse events of special

interest (see Section 5.2.2), adverse events leading to treatment discontinuation, and/or modification will be summarized.

Laboratory abnormalities will be summarized by treatment arm and grade.

Changes in selected vital signs will be summarized by treatment arm.

Deaths and causes of death reported during the study treatment period and those reported during the follow-up period after treatment completion/discontinuation will be summarized by treatment arm.

In addition, safety data will be presented in summary tables split by subgroups defined by age, sex, and race/ethnicity, as well as other potential risk factors as appropriate. Additional details will be provided in the SAP prior to performing the analyses.

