**Table 1 Objectives and Corresponding Endpoints (cont.)**

Safety Objective	Corresponding Endpoints

 
•To evaluate the safety and tolerability of atezolizumab and enzalutamide compared with enzalutamide alone
 
	
 
•Incidence, nature, frequency, and severity of adverse events, with severity determined through use of the National Cancer Institute Common Terminology Criteria for Adverse Events (NCI CTCAE v4.0)
 
•Clinically significant changes in vital signs, and clinical laboratory results during and following study treatment administration
 

Pharmacokinetic Objectives	Corresponding Endpoints

 
•To characterize the pharmacokinetics of atezolizumab when given in combination with enzalutamide
 
•To characterize the pharmacokinetics of enzalutamide and its active metabolite N-desmethyl enzalutamide when enzalutamide is administered alone or in combination with atezolizumab
 
	
 
•Serum concentration of atezolizumab at specified timepoints
 
•Plasma concentration of enzalutamide and N-desmethyl enzalutamide at specified timepoints in the safety run-in phase and in a PK cohort in the randomized phase (approximately 30 patients per treatment arm)
 

Exploratory Biomarker Objective	Corresponding Endpoints

 
•To identify biomarkers that are predictive of response to atezolizumab and/or enzalutamide (i.e., predictive biomarkers), are associated with progression to a more severe disease state (i.e., prognostic biomarkers), are associated with acquired resistance to atezolizumab and/or enzalutamide, are associated with susceptibility to developing adverse events, can provide evidence of atezolizumab and/or enzalutamide activity, or can increase the knowledge and understanding of disease biology on the basis of the following endpoint:
 
	
 
•Relationship between biomarkers in blood, urine, and tumor tissue (listed in Section 4.5.6) and efficacy, safety, PK, immunogenicity, or other biomarker endpoints
 

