## Randomized Phase

Enrollment in the randomized phase of the study will be initiated after review of the safety run-in data by the iDMC and the Sponsor. Approximately 720 patients will be enrolled in the randomized phase of the study. Patients will be randomized to one of the following treatment arms in a 1:1 ratio (experimental to control arm):

- Arm A (experimental arm): atezolizumab in combination with enzalutamide
- Arm B (control arm): enzalutamide alone

Randomization will be conducted with the aid of an interactive voice/Web response system (IxRS).

The randomization will be stratified by the following stratification factors:

- Prior taxane-containing regimen for mCRPC, defined as at least two cycles of a taxane-containing regimen (yes vs. no)
- Presence of liver metastasis (yes vs. no)
- LDH  $\leq$  upper limit of normal (ULN) vs.  $>$  ULN
- Pain severity (BPI-Short Form [SF] Question 3 assessing pain at its worst over the past 24 hours [score  $<$  4 vs.  $\geq$  4]) ([Appendix 7](#))

A stratified permuted-block randomization will be implemented to balance treatment assignment within stratum levels.

Patient recruitment will be capped with respect to two of the stratification factors: the proportion of patients who have not received a prior taxane-containing regimen for mCRPC will be approximately 50% or less, and the proportion of patients with liver metastases at baseline will be approximately 10% or less. Presence of liver metastases will be determined based on CT or MRI scan. The purpose of the cap is to ensure the prevalence of these two prognostic factors in the study population will be similar to that reported in the targeted population.

Atezolizumab will be administered at a fixed dose of 1200 mg by IV infusion on Day 1 of each 21-day cycle until investigator-assessed confirmed radiographic disease progression per PCWG3 or unacceptable toxicity.

Enzalutamide will be administered orally at a dose of 160 mg (four 40-mg capsules) daily until investigator-assessed confirmed radiographic disease progression per PCWG3 or unacceptable toxicity.

Patients will be permitted to continue study treatment after PCWG3 criteria are met for confirmed radiographic disease progression if they meet all of the following criteria (treatment until they are no longer clinically benefiting per PCWG3 recommendation [Scher et al. 2016]).

- Evidence of clinical benefit as assessed by the investigator

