#### **5.1.2 Risks Associated with Enzalutamide**

Enzalutamide has been associated with risks such as the following: seizures, falls, non-pathologic fractures, cognitive disorder, PRES, neutropenia and hypertension. For further adverse reactions, warnings, and precautions for enzalutamide, see local prescribing information.

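### Adverse events are tabulated by arm and grade only, although time at risk follows time on treatment; exposure-adjusted and time-to-first-event summaries should stand beside the raw tables

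*Combined protocol and SAP*

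**What the plan says.** The safety objective in Table 1 compares the two arms, and its first endpoint is "Incidence, nature, frequency, and severity of adverse events". Section 6.5 carries this out as follows: "All adverse events occurring during or after the first study-drug dose will be summarized by treatment arm and NCI CTCAE grade". Serious events, Grade 3 or higher events, events of special interest, and events leading to discontinuation or modification are also summarized.

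Exposure has its own sentence in the same section: "Exposure to study treatment will be summarized to include treatment duration, number of doses, and dose intensity". It is not linked to the event tables. Section 6.5 closes with "Additional details will be provided in the SAP prior to performing the analyses".

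Two other parts of the protocol determine time at risk:

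- **Treatment duration** (Section 3.1, Randomized Phase). Enzalutamide is given "daily until investigator-assessed confirmed radiographic disease progression per PCWG3 or unacceptable toxicity", and atezolizumab on "Day 1 of each 21-day cycle until investigator-assessed confirmed radiographic disease progression per PCWG3 or unacceptable toxicity". Treatment may also go past that point: "Patients will be permitted to continue study treatment after PCWG3 criteria are met for confirmed radiographic disease progression", subject to listed conditions.
- **Collection window** (Section 5.3.1). All adverse events are reported up to 30 days after the last dose. Serious events and events of special interest are reported up to 90 days. Either period ends sooner if new systemic anti-cancer therapy starts.

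Section 5.1.2 names the enzalutamide risks, to which both arms are exposed: "seizures, falls, non-pathologic fractures, cognitive disorder, PRES, neutropenia and hypertension".

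**The concern.** A patient who stays on drug longer is watched longer. Under these rules, the chance of recording a first event depends on the event hazard and on how long treatment lasts. If the arms differ in duration, a proportion with an event does not separate the two.

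Several features of the design could make duration unequal. Radiographic progression-free survival is a key secondary endpoint, so delayed progression is one of the effects under test. Continuing past progression rests on investigator-judged benefit in an open-label trial, and Section 3.4.8 justifies it partly by pseudoprogression under immunotherapy, which concerns Arm A only. Immune toxicity could shorten treatment in Arm A.

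Longer treatment in Arm A would inflate its raw incidence, and shorter treatment would hide a real excess. The effect is clearest for the shared enzalutamide risks, because a reader would take a difference there as an interaction between the two drugs.

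**Working it through.** **Starting point.** The documents give no numerical target for the safety comparison, so there is no planned safety figure to reproduce. The one borrowed design figure, the hazard ratio of 0.72 in Section 6.1, is consistent with its source: 12/16.7 = 0.719. The stated 97% power for 540 deaths also reproduces (96.8% by the Schoenfeld formula).

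**Inputs from the documents**

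- Control time to progression: about 3 months after two prior lines, and 8.1 months in the cited study of enzalutamide after abiraterone (both Section 1.1.2).
- 30-day reporting tail (Section 5.3.1): w = 30/30.4375 = 0.986 months.
- 720 patients randomized 1:1, so 360 per arm (Section 6.1).

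**Assumptions, not document figures**

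- The event hazard λ is constant and equal in both arms.
- Time on drug is exponential with stop hazard μ and equals time to progression.
- Arm A's stop hazard is r × μ. The value r = 0.72 is taken over from overall survival; r = 0.85 is a milder case.

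**Formula.** Raw incidence = 1 − exp(−λw) × μ/(μ + λ). λ is solved so that control incidence is 20%. Arm A then uses rμ in place of μ.

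| Control median | μ = ln 2/median | λ | exp(−λw) | Arm A, r = 0.72 | Arm A, r = 0.85 |
|---|---|---|---|---|---|
| 3 months | 0.23105 | 0.04518 | 0.95644 | 1 − 0.95644 × 0.16636/0.21154 = 24.8% | 1 − 0.95644 × 0.19639/0.24157 = 22.2% |
| 8.1 months | 0.08557 | 0.01937 | 0.98109 | 1 − 0.98109 × 0.06161/0.08098 = 25.4% | 1 − 0.98109 × 0.07274/0.09211 = 22.5% |

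With r = 1 both arms show 20%.

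**Opposite direction.** If Arm A stops sooner by the same factor (r = 1/0.72), 20% becomes 1 − 0.95644 × 0.32090/0.36608 = 16.2% at the 3-month median, and 1 − 0.98109 × 0.11885/0.13822 = 15.6% at 8.1 months.

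**Other incidences at r = 0.72.** The excess is 1.5–1.7 points at 5% control incidence and 6.9–7.6 points at 50%. If someone applied a nominal 5% two-proportion test with 360 per arm, it would be significant in 34–40% of trials at 20% incidence. That only conveys size, since no such test is planned.

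**Early-onset events.** Suppose all the hazard falls in the first 2 months, with r = 0.72. Then 20% becomes 20.1–20.3% and 50% becomes 50.2–50.6%, an excess of 0.1–0.6 points.

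**Does a person-time rate repair this?** Under a constant hazard it does: the rate ratio is 1.00 in every scenario above. Under the early-onset pattern it does not. Taking the rate as P(first event)/E(time at risk), with control incidence 10% or 20% and r = 0.72:

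| True hazard ratio | Raw incidence ratio | Rate ratio |
|---|---|---|
| 1.0 | about 1.01 | 0.74–0.78 |
| 1.3 | 1.27–1.30 | 0.98–1.04 |

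Late, event-free person-time dilutes the rate. Raw incidence fails for continuing hazards and the rate fails for early ones, so neither measure is enough alone.

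**The case against.** The strongest reply is that the premise is not in the plan. The documents assume no effect on progression or on treatment duration; 0.72 is for overall survival only. Section 1.1.1 describes a prostate immunotherapy that lengthened survival by a median of 4.1 months with similar time to progression in both groups, so a survival gain need not mean longer treatment. Progression is also not the same as stopping: treatment may continue past it, and Section 4.6.1 lists other reasons to stop. All of this stands. It makes the figures conditional, but it does not remove the dependence of time at risk on time on drug.

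Second, the plan summarizes duration, doses and dose intensity, and Section 3.2 gives the monitoring committee exposure data. An imbalance would therefore be visible. That also stands, but seeing an imbalance does not correct an event proportion for it.

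Third, the summaries are descriptive, with no between-arm test, and detail is deferred to the SAP. Exposure adjustment is therefore unspecified, not excluded. The objective is still comparative, and incidences set side by side will be read as a comparison.

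A reader might infer that Arm A will show excess toxicity caused by longer exposure alone. The documents do not support that. They do not say Arm A will be treated longer, the bias can reverse, and Arm A adds a second drug, so an observed excess would mix drug effect with duration. The recorded closure for futility (Section 3.3) does not settle treatment duration either way.

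**Conclusion.** The point holds in limited form. Section 6.5 specifies no event measure that accounts for time at risk, and the treatment and reporting rules tie that time to treatment duration. If duration differs, raw incidence of later or continuing events is distorted. Under the stated assumptions the distortion is about 5 points on a 20% incidence at a stop-hazard ratio of 0.72, about 2 to 2.5 points at 0.85, and about nil with equal exposure or early-onset events. The sign follows whichever arm is treated longer.

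These sizes rest on a constant equal hazard, exponential time on drug, and a ratio that the documents give for survival and not for treatment duration. A reader might also conclude that an exposure-adjusted rate should replace raw incidence as the basis for comparing the arms. The early-onset calculation shows why it should not: that rate can hide a true 30% excess. This is a cheap improvement and not a flaw that invalidates the safety analysis.

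**What to change.** In Section 6.5, keep the raw tables and add two supplementary summaries beside them, for each special-interest category and each risk named in Sections 5.1.1 and 5.1.2:

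- **(a) Exposure-adjusted rate.** Patients with a first event per 100 patient-years at risk, counted from first dose to first event or the end of the reporting window, with the arm rate ratio and 95% CI.
- **(b) Cumulative incidence of first event by arm over time.** State how death and the end of the reporting window are handled. Death would naturally be a competing event. If the end of the window is also treated as competing, the curve ends at the raw proportion and should be compared at fixed times. If it is treated as censoring, the text should say that this assumes stopping is unrelated to event risk.

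State that the measures are read together and that none is decisive alone.

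The cost is a little programming, using event and dosing dates already collected. The drawback is that (a) assumes a roughly constant hazard and can mislead for early-onset events, which is why (b) goes with it. No dose, treatment or clinical rule changes.

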## **6.6 PHARMACOKINETIC ANALYSES**

PK analyses will be performed on the PK-evaluable population, which is defined as patients who have received at least one dose of study drug and have at least one post-dose PK sample. The PK population for each study drug and specific timepoint will vary, depending on the availability of results with adequately documented dose time and PK sampling time.

Atezolizumab serum concentration data (minimum [ $C_{min}$ ] and maximum [ $C_{max}$ ]) will be reported and summarized (e.g., mean, standard deviation, coefficient of variation [CV%], median, range, geometric mean, geometric mean coefficient of variation [CVb]) for each cycle where collected as appropriate.

Plasma concentrations of enzalutamide and N-desmethyl enzalutamide will be reported and summarized using descriptive statistics as described above for each cycle and treatment arm, as appropriate. Data may be excluded from PK analysis if a patient has taken concomitant medications that are known to affect enzalutamide PK (see [Appendix 13](#)). For patients enrolled in China, plasma samples for enzalutamide and N-desmethyl enzalutamide will not be collected.

Additional PK and pharmacodynamic analyses will be conducted as appropriate on the basis of the available data.

## **6.7 IMMUNOGENICITY ANALYSES**

The immunogenicity analyses will include all patients enrolled, with patients grouped according to treatment received.

The numbers and proportions of ATA-positive patients and ATA-negative patients at baseline (baseline prevalence) and after baseline (post-baseline incidence) will be summarized by treatment group. When determining post-baseline incidence, patients

are considered to be ATA positive if they are ATA negative or are missing data at baseline but develop an ATA response following study drug exposure (treatment-induced ATA response), or if they are ATA positive at baseline and the titer of one or more post-baseline samples is at least 0.60-titer units higher than the titer of the baseline sample (treatment-enhanced ATA response). Patients are considered to be ATA negative if they are ATA negative or are missing data at baseline and all post-baseline samples are negative, or if they are ATA positive at baseline but do not have any post-baseline samples with a titer that is at least 0.60-titer units higher than the titer of the baseline sample (treatment unaffected).

The relationship between ATA status and safety, efficacy, PK, and biomarker endpoints may be analyzed and reported via descriptive statistics.

## **6.8 INTERIM ANALYSES**

### **6.8.1 Planned Interim Analyses**

A total of two analyses of OS will be performed: one interim analysis and the final analysis.

The interim analysis of the primary endpoint of OS will be performed when approximately 432 deaths have occurred (60% of 720 patients), corresponding to approximately 80% of the 540 deaths required for the final analysis of OS. The required number of deaths for the interim analysis is projected to occur at approximately Month 27 after randomizing the first patient.

The Lan-DeMets alpha-spending function approach will be used to determine the boundary values for statistical significance at the interim and final analysis (DeMets and Lan 1994).

For the primary endpoint of OS, the stopping boundaries will be based on the O'Brien-Fleming alpha-spending function. At both the interim and final OS analysis, key secondary endpoints listed in Section 6.4.2 will be evaluated for statistical significance only if the difference in duration of OS is statistically significant at the appropriate boundary level. For these secondary endpoints, the boundaries for statistical significance will be based on a Pocock alpha-spending function. Key secondary endpoints will be tested at the appropriate significance level in the order specified in Section 6.4.2. If for one endpoint in this list the null hypothesis cannot be rejected, then the results for this and all following endpoints are not statistically significant.

The hierarchical testing procedure with the boundaries determined as described above ensures that the overall type I error for the primary and key secondary endpoints will be controlled at 0.05 (Hung et al. 2007; Glimm et al. 2010).

The interim OS analysis will be performed by the iDCC and reviewed by the iDMC (see Section 3.2). The Sponsor will remain blinded to the results. On the basis of its review

of the data, the iDMC will provide a recommendation as to whether to release the study results early because of substantial evidence of efficacy.

### **6.8.2 Optional Interim Analysis**

To adapt to information that may emerge during the course of this study, the Sponsor may choose to conduct one interim efficacy analysis for the primary endpoint of OS beyond what is specified in Section 6.8.1. The decision to conduct the optional interim analysis, along with the rationale, timing, and statistical details for the analysis, will be documented in the SAP, and the SAP will be submitted to relevant health authorities at least 2 months prior to the conduct of the interim analysis.

If an interim analysis is conducted, the Sponsor will remain blinded. The interim analysis will be conducted by the iDCC and reviewed by the iDMC. Interactions between the iDMC and Sponsor will be carried out as specified in the iDMC Charter.

If there is a potential for the study to be stopped for positive efficacy as a result of the interim analysis, the type I error rate will be controlled using the same Lan-DeMets approach as for the planned interim analysis described above.

